9.5. Variables

9.5.1. Baseline Data

The following information is collected within RABBIT, having been reported by the recruiting clinician, using a standardized form:

- 1. Diagnosis (including the presence or absence of those features listed in 1987 American College of Rheumatology (ACR) criteria for RA).
- 2. Age at treatment start, gender, year of recalled symptom onset, year of diagnosis.
- 3. Previous drug history of immunosuppressive conventional synthetic DMARDS (csDMARDs) and biologics, biosimilar or other new advanced therapy since enrolment, including duration of therapy recorded as start month/year and reasons for interruption.
- 4. Co-morbidity calculating the Charlson index.
- 5. All current therapy.

b. Patients are ineligible for bDMARD cohort index after tofacitinib index.

- 6. Baseline disease activity including Disease Activity Score (DAS)-28, Health Assessment Questionnaire (HAQ); Pain Visual Analog Scale (VAS), Global Health VAS, Tender Joint Count, Swollen joint count, C-reactive protein (CRP), erythrocyte sedimentation rate (ESR), American College of Rheumatology (ACR) rating scale.
- 7. Baseline history of disease including tuberculosis, serious infection, malignancy, heart disease.

9.3.2 Follow-up

Follow up data in RABBIT derive from follow-up visits at months 3, 6, 12, 18, 24, 30, 36, 48, 54, and 60.

All serious and non-serious events occurring during the observation are regularly reported from the rheumatologist and captured in the register (with judgement from the rheumatologist on: severity (mild, moderate, severe; and causality to given medication). For events of special interest detailed queries are sent out, to get more information on the events (and additional discharge letters from hospitals, or results from biopsies etc). The actual events of interests are: Serious infections, Tuberculosis, Lymphomas, Aplastic Anaemia/Pancytopenia, Demyelinating Diseases, (Congestive) Heart Failure, Gastrointestinal ulcers and perforations, Malignancies, Myocardial infarction, Stroke, Serious hepatic events/hepatic failure, Serious hypersensitivity reactions, Pregnancies, Death.

There is no possibility to link RABBIT data with any other data due to strict data protection rules and due to the fact that there is no national cancer register or death register with the possibility of linkage. However, all events are carefully monitored and several national offices are sometimes contacted to get more information.

9.3.3 Endpoints

Endpoints in RABBIT derive from physician reports of the occurrence of any AE or event of special interest. The events of interest, based on previously identified risks in the treated and untreated RA population, include:

- 1. Serious infections (excluding TB): pneumonia, other infections of the respiratory system, infections of the CNS, sepsis, bone or joint infections, OI, other infections.
- 2. TB.
- Herpes Zoster.
- 4. Cardiac disorders: heart failure, coronary artery disease, myocardial infarction, other cardiac disorders.
- 5. Hematologic disorders: bone marrow depression and hypoplastic anaemia, decreased white blood cells, platelet disorders, other blood dyscrasia.

- Disorders of the nervous system (excluding infections): stroke, central demyelination, other disorders of the CNS, disorders of the peripheral nervous system, psychiatric disorders.
- 7. Progressive multifocal leukoencephalopathy.
- 8. Allergic conditions and hypersensitivity.
- 9. Hepatic failure.
- 10. Gastrointestinal (GI) perforations.
- 11. Pregnancy.
- 12. Thromboembolic events: deep vein thrombosis (DVT) and pulmonary embolism (PE).
- 13. Operations and hospitalisations: bone and joint surgery and other joint therapeutic procedures, other operations and (major) therapeutic procedures that lead to hospitalization.
- 14. Other serious diagnoses, symptoms, and syndromes.
- 15. NMSC.
- 16. Malignancies, excluding NMSC.
- 17. All-cause Mortality.

Rates of these endpoints of interest and their 95% CI will be reported for tofacitinib exposed and comparator cohorts every six months.

9.4 Data Sources

Core baseline and follow up data, including patient demographics, disease characteristics, and treatment will be based on data from the RABBIT.

9.6. Study Size

This active surveillance study is not intended to test a pre-specified statistical hypothesis. The size of the active surveillance population depends largely on use of tofacitinib in Germany. The targeted sample size for tofacitinib-treated patients is 500. Enrolment will not be capped at 500 but continue throughout the study period.

The bDMARD and nbDMARD populations used to contextualize event rates are well-established.

While the primary objective of the protocols is active surveillance, conducting quantitative, confounding controlled comparisons will depend on having a sufficient sample.

Table 1 and Table 2 below describe the power to detect a 2-fold difference in event rates between tofacitinib-initiators and bDMARD-initiators assuming the following:

- $\alpha = 0.05$;
- 3 different bDMARD-treated patient population sizes (reflecting roughly range of EU registers): n=11 100, n=5050, n=1650;
- 4 different tofacitinib-treated patient population sizes: n=100, n=250, n=500, n=1000;
- Estimated rates on bDMARD of 30/1000 person years (PY) (eg, serious infection), 10/1000 PY (eg, malignancy excluding NMSC), and 6/1000 PY (eg, major adverse cardiovascular events (MACE) based on previous analysis with registers (Pfizer, internal data);
- 7-year study period;
- Constant rate of accrual;
- 5% annual loss to follow up among to facitinib-treated patients.

Additionally, Table 1 assumes a 0% annual rate of switching off to facitinib, as would be true for a drug with very high persistence or for an analysis following the once exposed always at risk paradigm (see Question 8). Table 2 assumes a 30% annual rate of switching from to facitinib to a bDMARD over the study period, as previously demonstrated in the EU for bDMARDs in Italy (Eposti, 2016).²⁹

For an event with a rate of 30/1000 PY, such as serious infections, 250 patients would allow sufficient power to detect a 2-fold difference in rates between tofacitinib and bDMARD-exposed patients assuming very high persistence (Table 1), while 500 tofacitinib exposed patients would be nearly sufficient if 30% of tofacitinib treated patients switched off of tofacitinib annually.

For an event with a rate of 10 cases per 1000 PY, such as malignancy excluding NMSC, a sample of 500 patients approaches 80% power in a medium (n=5050) to large (n=11,100) register when patient time continues to accrue after drug discontinuation (Table 1). It will be a challenge to achieve sufficient power in a register with fewer bDMARD exposed patients. Nonetheless, replication of a similar trend in an underpowered sample could be locally informative.

For an endpoint with an event rate of 6/1000 PY, such as MACE, even assuming high persistence (Table 1) a sample size of 1000 tofacitinib patients within a registry with more than 5000 bDMARD patients would be required to make well-powered comparison. In a scenario with a 30% annual rate of switching off of tofacitinib, 1000 tofacitinib treated patients and 11 100 bDMARD patients would only provide 40% power to detect a 2-fold difference (Table 2).

Prior to conducting any analyses, a feasibility assessment will be conducted to determine the approximate power of planned comparative analyses.

Table 1. The Power To Detect A Two-Fold Difference In Risk Among Tofacitinib Exposed Patients Compared With bDMARD-Treated Register Patients Given Different Assumed Sample Sizes, alpha = 0.05, 5-Year Study With Uniform Accrual, 5% Loss To Follow Up Per Year In Tofacitinib Arm

Number of tofacitinib exposed	~11100	~5050	~1650
patients	bDMARD-treated	bDMARD-treated	bDMARD-treated
	patients	patients	patients
bDMARD rate ~30/1000 PY			
(eg, serious infections)			
100	0.46	0.45	0.44
250	0.92	0.91	0.88
500	1.00	1.00	0.99
1000	1.00	1.00	1.00
bDMARD rate ~10/1000 PY			
(eg, malignancy)			
100	0.11	0.12	0.12
250	0.38	0.38	0.36
500	0.75	0.73	0.66
1000	0.98	0.96	0.89
bDMARD rate ~6/1000 PY			
(eg, MACE)			
100	0.06	0.06	0.06
250	0.20	0.20	0.20
500	0.47	0.46	0.41
1000	0.83	0.79	0.68

Table 2. The Power To Detect A Two-Fold Difference In Risk Among Tofacitinib Exposed Patients Compared With bDMARD-Treated Register Patients Given Different Assumed Sample Sizes, alpha = 0.05, 5-Year Study With Uniform Accrual, 5% Loss To Follow Up Per Year In Tofacitinib Arm, 30% Switch From Tofacitinib To bDMARD Per Year

Number of tofacitinib	~11100	~5050	~1650
exposed patients	bDMARD-treated	bDMARD-treated	bDMARD-treated
	patients	patients	patients
bDMARD rate ~30/1000 PY	-	-	
(eg, serious infections)			
100	0.18	0.18	0.18
250	0.50	0.49	0.46
500	0.84	0.82	0.75
1000	0.99	0.98	0.93
bDMARD rate ~10/1000 PY			
(eg, malignancy)			
100	0.06	0.06	0.06
250	0.16	0.16	0.15
500	0.33	0.32	0.30
1000	0.64	0.60	0.50
bDMARD rate ~6/1000 PY			
(eg, MACE)			
100	0.04	0.04	0.04
250	0.09	0.09	0.09
500	0.19	0.19	0.18
1000	0.40	0.38	0.32

Based on the first 16 months of enrolment of tofacitinib-exposed patients in RABBIT, 558 patients are projected to be enrolled in the first 24 months, allowing at least 5 years follow up by the end of the planned study period, assuming the initial rate remains constant over the period.

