Using this primary analytic approach, if neither tofacitinib nor bDMARDs cause an increased risk of malignancy both exposure cohort rates will reflect the background rates of malignancy from the time of index to the end of the study period and the comparative effect measure will indicate no difference in rates. If tofacitinib does cause an increased rate of malignancy, which is the effect we are most interested in detecting, a relatively higher rate will be observed in the tofacitinib exposed cohort. The once exposed always at risk approach is therefore able to detect an increased rate given the non-random switching expected to occur given use of bDMARDs prior to tofacitinib and is consistent with previous studies evaluating the risk of individual biologics. Additional analyses will be conducted to evaluate potential confounders and the impact of different latency assumptions as will be described in the SAP. Sensitivity analyses will be conducted that restrict the bDMARD comparator cohort to patients who were never exposed to tofacitinib or other non-biologic advanced therapies and compare the characteristics of those bDMARD patients ever and never exposed to tofacitinib.

Secondary analyses that censor follow up time after a switch to a different treatment class will also be performed. Among patients indexed to a bDMARD cohort, follow up will begin at index and continue until the first of an event, switch to tofacitinib or other non-biologic advanced systemic therapy, loss to follow up, death, or study end date. Similarly, for tofacitinib, follow up will begin at index and continue until the first of an event, switch to a non-JAK inhibitor-based advanced systemic therapy, loss to follow up, death or study end date. While this approach eliminates the problem of double counting, it may not allow sufficient follow up time to allow for latent effects or detection and decreases the number of events included reducing the statistical power to detect a higher risk of malignancy in tofacitinib treated patients. However, under an assumption of no latency or a very short latent period as in an aggressive tumor promoter, this approach would detect an increased risk of disease on tofacitinib relative to the risk due to bDMARDs.

Of note, several studies compared a once-exposed approach to a time on drug and other approaches and found similar rates of malignancy using an on-drug and ever-exposed approach. ^{26,14,15}

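### The powers in Tables 1 and 2 do not follow from the stated inputs for a doubling of the event rate on tofacitinib; they match a calculation for a halving, and power to detect an excess is mostly understated

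*Protocol*

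**What the plan says.** Protocol section 9.6 (Study Size) introduces two power tables that "describe the power to detect a 2-fold difference in event rates between tofacitinib-initiators and bDMARD-initiators assuming the following". The listed inputs are:

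- "Estimated rates on bDMARD of 30/1000 person years (PY) (eg, serious infection), 10/1000 PY (eg, malignancy excluding NMSC), and 6/1000 PY"
- "4 different tofacitinib-treated patient population sizes: n=100, n=250, n=500, n=1000"
- "3 different bDMARD-treated patient population sizes (reflecting roughly range of EU registers): n=11 100, n=5050, n=1650"

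Both table titles begin "The Power To Detect A Two-Fold Difference In Risk Among Tofacitinib Exposed Patients Compared With bDMARD-Treated Register Patients" and add "alpha = 0.05, 5-Year Study With Uniform Accrual, 5% Loss To Follow Up Per Year In Tofacitinib Arm". Table 2 adds a 30% annual switch from tofacitinib to bDMARD. The bulleted list gives a 7-year study where the titles give 5 years.

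The text then judges endpoints by these figures. For MACE with switching, for example, it says that "1000 tofacitinib treated patients and 11 100 bDMARD patients would only provide 40% power to detect a 2-fold difference".

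Section 9.4 (Risk Window) gives the direction that matters: "If tofacitinib does cause an increased rate of malignancy, which is the effect we are most interested in detecting".

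**The concern.** The bDMARD rates are fixed inputs, so the alternative that serves the safety aim is tofacitinib at twice those rates. Section 9.6 never says so, and a two-fold difference can equally mean a halving. When one arm is far smaller than the other, the two directions give very different power, because the small arm supplies most of the variance.

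Two features of the tables prompt the question. Table 2 prints 0.04 for MACE at n=100, below the alpha of 0.05. In Table 1, malignancy at n=100 rises from 0.11 to 0.12 as the comparator shrinks from 11,100 to 5,050. A pooled-variance formula produces both when the small arm has the lower rate.

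Section 9.6 promises a feasibility assessment of power before any analysis, and section 9.8 makes the final comparison depend partly on power. If the same calculation is carried forward, it will tend to understate the ability to see harm and could count against the malignancy or CV comparisons.

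**Working it through.** **Inputs.** Rates, sample sizes, alpha, the 5-year study, 5% loss on tofacitinib only and 30% switching are from section 9.6. My assumptions are exponential event times, a two-sided test, loss and switching as hazards of 0.05 and 0.30 per year, switchers taking the bDMARD rate, and the accrual length A. Follow-up u is uniform on [5−A, 5].

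**Formula.** For bDMARD, p_b is the mean of 1 − exp(−λ_b·u). For tofacitinib without switching, p_t is the mean of λ_t/(λ_t+0.05) × [1 − exp(−(λ_t+0.05)u)]. With pooled proportion p̄,

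se0 = √[p̄(1−p̄)(1/n_t + 1/n_b)], se1 = √[p_t(1−p_t)/n_t + p_b(1−p_b)/n_b],

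power = Φ[(|p_t − p_b| − 1.96·se0)/se1].

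**Printed figures, with tofacitinib at half the rate and A = 2.**

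- Table 1, malignancy, 500 vs 11,100: λ_b = 0.010, λ_t = 0.005. Mean exp(−0.01u) = (0.97045 − 0.95123)/0.02 = 0.9608, so p_b = 0.0392. Mean exp(−0.055u) = (0.84789 − 0.75957)/0.11 = 0.8029, so p_t = 0.1971 × 0.005/0.055 = 0.0179. Then p̄ = 0.0383, se0 = 0.00877, se1 = 0.00621. Power = Φ[(0.02128 − 0.01719)/0.00621] = Φ(0.66) = 0.745; printed 0.75.
- Table 2, MACE, 1000 vs 11,100: with switching, p_t = 0.01516 and p_b = 0.02371; se0 = 0.00495, se1 = 0.00413. Power = Φ[(0.00855 − 0.00970)/0.00413] = Φ(−0.28) = 0.39; printed 0.40.
- Table 2, MACE, 100 vs 11,100: se0 = 0.01526, se1 = 0.01230. Power = Φ[(0.00855 − 0.02991)/0.01230] = Φ(−1.74) = 0.041; printed 0.04.

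Over both tables all 72 cells agree within 2 points (worst 1.7). A 7-year study with 6-year accrual matches 71 of 72.

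**Same formula, tofacitinib at twice the rate, A = 2.** Malignancy, 500 vs 11,100: p_t = 0.0696, p̄ = 0.0405, se0 = 0.00901, se1 = 0.01153. Power = Φ[(0.03040 − 0.01767)/0.01153] = Φ(1.10) = 0.87, against 0.75 printed. Other formulas were tried for a doubling (Schoenfeld, Freedman, Lakatos, Wald on the log rate ratio, log rate ratio with null variance, rate difference, exact conditional). The best joint fit, the log scale with null variance and 4.5-year accrual, matched 59 of 72 cells, worst error 4.5 points.

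**Power for a doubling, exact conditional test.** Given all events, the tofacitinib count is binomial. Its null share is q = Y_t/(Y_t+Y_b), where Y is person-time. Its share under the alternative is E_t/(E_t+E_b), where E is expected events. Power is averaged over a Poisson total. Example, Table 1 malignancy n=500, A = 5: Y_t = 500 × 2.232 = 1,116; Y_b = 11,100 × 2.459 ≈ 27,295; q = 0.039; E_t = 22.3; E_b = 272.9; alternative share 0.076; power 0.76.

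With 11,100 bDMARD patients, a 5-year study and 5% loss:

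| Cell | Printed | A = 5 | A = 2 |
|---|---|---|---|
| Table 1 MACE n=100 | 0.06 | 0.14 | 0.22 |
| Table 1 MACE n=500 | 0.47 | 0.54 | 0.74 |
| Table 1 MACE n=1000 | 0.83 | 0.82 | 0.95 |
| Table 1 malignancy n=100 | 0.11 | 0.21 | 0.32 |
| Table 1 malignancy n=500 | 0.75 | 0.76 | 0.91 |
| Table 2 malignancy n=500 | 0.33 | 0.45 | 0.56 |
| Table 2 MACE n=1000 | 0.40 | 0.51 | 0.63 |
| Table 2 MACE n=100 | 0.04 | 0.08 | 0.10 |

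With A = 5, 12 of the 72 cells fall slightly below the printed value, by about 3 points at most. All are Table 1 cells at n=250 or more. With A = 2 none do.

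**The case against.** The strongest reply is that the halving fit rests on an accrual length the protocol does not give. Section 9.6 says enrolment continues throughout the study period. With accrual over all 5 years, the halving formula gives p_b = 0.0246, p_t = 0.0114 and power Φ[(0.01316 − 0.01372)/0.00498] = Φ(−0.11) = 0.46 for malignancy at n=500, a miss of 29 points. A log-scale calculation for a doubling then does better, within about 8 points on both tables. If 30% switching is coded as −ln 0.7 per year, only 17 of 36 Table 2 cells match under a halving. All this stands: the fit supports an inference, not proof.

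Nor do the odd cells prove a halving. Normal-approximation formulas count one tail, so 0.04 is possible. An unpooled Wald rate-difference test of a doubling, with 2.5 PY per patient and no loss, gives 0.034 to 0.037 for MACE at n=100, and fits Table 1 within about 3 points. It does so only without the stated loss. A step from 0.11 to 0.12 is one rounding unit.

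It is also fair that the study is descriptive, that no sample size is set from these tables, that a fresh feasibility assessment is planned, and that the error mostly errs low. With 5-year accrual most text conclusions survive: malignancy at n=500 still approaches 80% in Table 1, and MACE still needs about 1000 patients.

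None of this makes the tables follow from their stated inputs. Full 5-year accrual breaks the halving fit, but it does not give the printed values for a doubling either.

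**Conclusion.** The point holds in a limited form. The printed powers are not what the listed inputs give for a doubling on tofacitinib, the effect section 9.4 puts first. They agree with a halving in all 72 cells under one plausible configuration.

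A reader might infer that the tables were certainly computed in the wrong direction, that values such as 0.04 are impossible for a doubling, or that every conclusion in section 9.6 is wrong. The document supports none of these. It states no direction, test or accrual length, and a two-fold difference literally covers a halving.

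The understatement is largest, relative to the printed value, at small n, for rare events and in Table 2. At the target of 500 patients, with 11,100 bDMARD patients, it is 7 to 27 points for Table 1 MACE (0.54 to 0.74 against 0.47) and 12 to 23 points for Table 2 malignancy (0.45 to 0.56 against 0.33). The 40% quoted for MACE becomes 51% to 63%, still short of 80%. Table 1 malignancy at n=500 barely moves with 5-year accrual and reaches 0.91 with 2-year accrual. These ranges rest on a two-sided exact test, a 5-year study and the hazard coding above. The correction is worth making, but it does not undermine the study.

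**What to change.** In section 9.6, state the direction (rate ratio 2 on tofacitinib, bDMARD at the listed rates), the sidedness, the test, the accrual length and a single study length. Recompute both tables on that basis with the stated 5% loss and, for Table 2, a stated handling of the 30% switch. An exact conditional or score test for a rate ratio would do; what matters is that the test is named and holds its 5% level.

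Restate the power sentences for serious infection, malignancy and MACE wherever the new values change them, including the 40% figure. Use the same direction and test in the pre-analysis feasibility assessment and in the 7-year feasibility decision in section 9.8.

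The cost is a recalculation and revised text in one section. Patients, data collection and endpoints are unaffected. The 5- versus 7-year mismatch can be settled in the same edit.

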9.4. Risk Window

Within each cohort, each patient will be evaluated for safety events of interest while exposed to the index therapy and accrue person-time from the cohort index date until the first occurrence of the event of interest, discontinuation of index treatment, death, loss to follow up, exit from the register or after 7 years of follow up. Interim reports will not censor the existing comparison cohorts to match the tofacitinib cohort on index date or duration of follow up. The final report will censor all patients at 7 years. Follow-up will be uniquely determined for each safety endpoint of interest.

Some outcomes of interest in this study are thought to potentially occur at a higher rate while on drug, but that increased risk subsides after the drug is discontinued (ie, serious infections, herpes zoster, CV events, gastrointestinal (GI) perforation, progressive multifocal leukoencephalopathy (PML). Those events will be evaluated over a risk window that includes time from drug initiation until 90 days after end of treatment. When a patient initiates a new therapy within the 90-day extension, the time and events during the overlapping period will be assigned to both treatments. The 90-day extension period is implemented in part to accommodate ongoing exposure to treatments with longer half-lives, and in part to ensure that any subclinical or undiagnosed illness at time of end of treatment is captured.

For non-melanoma skin cancer (NMSC) and malignancies, the manifestation of which is expected to be delayed relative to the time of exposure, the outcomes will be evaluated using two different approaches, a once exposed always at risk approach as the primary analysis and a censor at switch approach as a secondary analysis. PML rates will also be described using this approach.

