The feasibility of conducting a final comparative study will be evaluated at 7-years of follow up based on statistical power and suitable overlap in patient populations in the exposure groups. Any final comparative report will adjust for differences in severity of disease and other confounders will be completed using appropriate multivariate, propensity score matching, or inverse probability weighting methods. For these analyses, the exposure cohorts will be analyzed overall, previous biologics use and monotherapy and combination therapy with concomitant conventional synthetic disease modifying antirheumatic drugs (csDMARDs). A combination therapy with MTX specifically will be described if sample sizes are sufficient. These and potentially other agreed upon strata will be determined apriori and included in SAP filed with Sponsor. The general analytic approach will be descriptive and include rates of events of interest within stratified treatment cohorts. Data will be presented as number of events, crude and age/sex-standardized incidence rates. Such analyses will be performed by and at the direction of RABBIT. The final report will also evaluate the rates of safety events of interest within the elderly. The approved SAP will also describe the a priori determined common set of MedDRA codes and the MedDRA version to define serious infections, GI perforations, herpes zoster, and CV events (MACE). The codes and version will be harmonised with other registers conducting similar analysis. A draft set of MedDRA codes is included in Appendix 1.

Meta-analytic methods that attempt to combine the results of this study with results from other participating European registers will be used to summarize the findings across studies. A quantitative meta-analysis would permit an estimate of an average effect across the studies with more statistical power than the individual studies, provided a formal evaluation did not reveal substantial heterogeneity. Meta-analysis may reveal between-study heterogeneity such that a subset of more comparable studies could be included in a single estimate. Heterogeneity may be expected, for example due to differences in local prescribing practices, patient populations, competing risks, and prevalence of comorbidities and risk factors. Such heterogeneity would exist even if the coding for endpoint definitions and reporting could be harmonized across registers. In the presence of such heterogeneity, pooling across the

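### Section 9.6 assumes a 7-year study but its power tables are 5-year figures, and Table 2 does not appear to model the planned on-drug analysis; the stated powers are too low for the study described.

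*Protocol*

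**What the plan says.** Section 9.6 (Study Size) reports "power to detect a 2-fold difference in event rates between tofacitinib-initiators and bDMARD-initiators" in Tables 1 and 2. The listed assumptions are alpha 0.05, "Estimated rates on bDMARD of 30/1000 person years (PY) (eg, serious infection), 10/1000 PY (eg, malignancy excluding NMSC), and 6/1000 PY" (the last for MACE), bDMARD cohorts of "n=11 100, n=5050, n=1650", constant accrual, 5% yearly loss in the tofacitinib arm and a "7-year study period". Both table titles, repeated in the List of Tables, instead read "5-Year Study With Uniform Accrual, 5% Loss To Follow Up Per Year In Tofacitinib Arm". Elsewhere (Abstract, 9.4 Risk Window, 9.8, 9.10, section 12) follow-up is 7 years. The section 6 milestones run from 15 September 2019 to 14 September 2025, which is 6 years.

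Table 1 has no switching and is tied to very high persistence or to the once-exposed analysis. Table 2 adds 30% yearly switching to a bDMARD, without saying how time after the switch is treated. From Table 2 the text concludes that "1000 tofacitinib treated patients and 11 100 bDMARD patients would only provide 40% power to detect a 2-fold difference" for MACE. Section 9.4 (Risk Window) counts serious infections and cardiovascular events over "time from drug initiation until 90 days after end of treatment". Section 9.8 makes the final comparison depend on feasibility "based on statistical power and suitable overlap in patient populations".

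**The concern.** The assumption list and the titles describe the same figures, so one of them is wrong, and the milestones give a third duration. Separately, under the on-drug window a switcher's person-time leaves the tofacitinib denominator after 90 days. Switching then costs follow-up, but the rate ratio under the alternative stays at 2. A table that leaves switchers in the arm at the comparator rate dilutes the ratio and answers a different question. What is at stake is whether the only power figures in the protocol, and the sentences drawn from them, describe this study.

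**Working it through.** **Inputs (section 9.6).** Rate ratio 2; bDMARD rates 30, 10 and 6 per 1000 PY; the cohort sizes above; 5% yearly loss in the tofacitinib arm only (hazard λ = −ln 0.95 = 0.0513); switching 30% per year (hazard s = −ln 0.70 = 0.357). Not stated and therefore assumed: two-sided test, accrual over the whole period T, no bDMARD loss or discontinuation, no removal of person-time after an event.

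**Formulas.** Mean person-years per patient are T/2 with no exits, otherwise (1/h)·[1 − (1 − e^(−hT))/(hT)] for total exit hazard h. With events E and person-years P in each arm and pooled rate r = (E1+E2)/(P1+P2), SE0 = √(1/(rP1) + 1/(rP2)), SE1 = √(1/E1 + 1/E2), and power = Φ[(ln RR − 1.96·SE0)/SE1].

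**Reproducing Table 1** (malignancy, 500 vs 5050; stated 0.73). At 5 years without loss, P = 1250 and 12 625, and E = 25 and 126.25. SE0 = 0.284, SE1 = 0.219, z = 0.62, power 0.73. With 5% loss (2.30 PY per patient) it is 0.69.

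| Table 1 model | Cells within 2 points | Largest miss |
|---|---|---|
| 5 years, no loss | 31 of 36 | 3.8 points |
| 5 years, 5% loss | 24 of 36 | 4.9 points |
| 7 years, 5% loss | 9 of 36 | 14 points |
| 7 years, no loss | 7 of 36 | 21 points |

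**Table 1 at 7 years, same cell.** No loss: P = 1750 and 17 675, E = 35 and 176.75, SE0 = 0.240, SE1 = 0.185, z = 1.20, power 0.89. With 5% loss: 3.12 PY per patient, E = 31.2 and 176.75, z = 1.00, power 0.84.

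| Malignancy, n=500 | vs 11 100 | vs 5050 | vs 1650 |
|---|---|---|---|
| Stated | 0.75 | 0.73 | 0.66 |
| 6 years (5% loss to no loss) | 0.79-0.84 | 0.78-0.82 | 0.73-0.77 |
| 7 years (5% loss to no loss) | 0.85-0.90 | 0.84-0.89 | 0.80-0.84 |

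**Reproducing Table 2 at 5 years.** Mean time in the study is 2.30 PY, of which 1.41 PY is before the switch (h = λ + s).

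- *Switchers kept in the arm at the bDMARD rate:* average ratio = 1 + 1.41/2.30 = 1.61. Serious infection 500 vs 5050: E = 55.6 and 378.75, power 0.83 (stated 0.82). MACE 1000 vs 11 100: E = 22.2 and 166.5, power 0.40 (stated 0.40). Overall 32 of 36 cells fit, largest miss 2.7 points.
- *Censored at switch, ratio 2:* 12 of 36 cells fit, with misses up to 23 points.

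**On-drug power (censored at switch).**

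| | Stated | 5 years | 7 years |
|---|---|---|---|
| Serious infection, 500 vs 5050 | 0.82 | 0.95 (E = 42.2, 378.75; z = 1.64) | 0.98 (E = 49.3, 530.25; z = 2.00) |
| MACE, 1000 vs 11 100 | 0.40 | 0.53 (E = 16.9, 166.5; z = 0.07) | 0.61 (E = 19.7, 233.1; z = 0.29) |

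**Sensitivity.** Removing person-time after a first event, with or without the 90-day extension (at the bDMARD rate or twice it), gives 0.92-0.95 and 0.95-0.98 for serious infection at 5 and 7 years, and 0.50-0.56 and 0.58-0.65 for MACE. Applying 30% yearly discontinuation to the bDMARD arm too barely changes these cells (MACE 0.52 at 5 years, 0.61 at 7). It matters more in the smallest register: MACE 1000 vs 1650 at 5 years falls from 0.49 to 0.47.

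**The case against.** The best defence is that little depends on these tables. The study is descriptive, enrolment is uncapped, the target of 500 is not derived from them, and the cohort sizes only roughly span European registers. Section 9.6 promises a power assessment before any analysis, and section 9.8 places the feasibility decision at 7 years. All of this stands. A reader might infer that a feasible comparison would be abandoned because of the printed figures; the documents do not make Tables 1 and 2 the basis of that decision.

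A reader might also infer that the statements about 250 patients for serious infections and 1000 for MACE rest on the wrong table. They do not: both are expressly conditional on high persistence, and the 30% switching scenario is set against each.

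The account of Table 2 is an inference from fit. Table 2 also separates 5 from 7 years less clearly: with person-time removed after events, the diluted model fits 34 cells at 5 years and 30 at 7. The duration point therefore rests on the titles and Table 1. Magnitudes depend on the test: an exact conditional test gives 0.63 for on-drug MACE, 1000 vs 11 100, at 5 years, but it also exceeds Table 1 by up to 8 points where no switching is involved, so part of that gap is the test.

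Could 5 years mean minimum follow-up, given the projection of 558 patients in 24 months? No: 2-year accrual within a 7-year study fits only 7 of 36 Table 1 cells.

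**Conclusion.** The 5- versus 7-year contradiction is in the text, and the arithmetic shows that Table 1 is a 5-year table. For a 7-year study the statement that 500 patients only approach 80% power for malignancy in medium and large registers is wrong, since power there is about 0.84-0.90. At 6 years it is borderline (0.78-0.84). Table 2 very probably describes a diluted comparison with a ratio of about 1.6, not the on-drug plus 90 days analysis. Under the planned window the two cells quoted in the text rise from 0.82 to 0.95-0.98 and from 0.40 to 0.53-0.61.

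These figures assume the test and accrual above, no bDMARD discontinuation unless noted, and no confounding adjustment. The once-exposed figures also ignore that section 9.4 (Risk Window) counts events after a switch to tofacitinib in the bDMARD cohort as well, which would dilute the ratio. The errors understate power and change no estimate or patient number, so severity is moderate.

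**What to change.** 1. Reconcile the study duration across the assumption list, both table titles (and the List of Tables) and the section 6 milestones.
2. Recompute Table 1 for the once-exposed analysis over that duration. Say whether the 5% loss is included; the printed figures fit better without it.
3. Recompute Table 2 for the on-drug plus 90 days analysis, with later post-switch time removed and the ratio kept at 2.
4. State the test and its sidedness, the accrual length, and how post-switch time and bDMARD discontinuation are handled.
5. Rewrite the sentences interpreting the tables from the new figures.

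The cost is a few hours of calculation and a wording change in section 9.6. No new patients or data are needed.
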